1. Current cannabis use: average of 2 cannabis cigarettes per day at least 6x/ week for the past 4 weeks	Self-report during clinical interviews (telephone, psychologist, physician), urine toxicology
2. Able to perform study procedures	Practice sessions, physician's physical and mental status examination
3. 21-50 years of age	Legal identification
4. Women practicing an effective form of birth control (condoms, diaphragm, birth control pill, IUD)	Self-report during clinical interview, physician's evaluation
5. English Speaking	Clinical interview, ability to complete screening paperwork
6. Able to give informed consent	Clinical interview, physician's mental status examination
Exclusion:	
1. Current diagnosis of an eating disorder (anorexia, bulimia, etc.) or have lost more than 10% of their body weight within the last 3 months and a known sensitivity, allergy or contraindication to lorcaserin or similar medications	Medical history, physical examination
2. Current, repeated (>2x/week) illicit drug use other than cannabis	Clinical interview, physicians evaluation, urine toxicology
3. Presence of any clinically significant cardiovascular, respiratory, renal, gastrointestinal, hematologic, neurologic, pulmonary, immunologic, hepatic, endocrine, or other abnormality	Medical history, physical examination, 12-lead ECG, laboratory tests (Chem panel, CBC, urinalysis)
4. History of heart disease and cardiac risk factors (congestive heart failure, edema, unstable angina, or cardiac arrhythmias), blood pressure > 140/90, severe chronic obstructive pulmonary disease, uncontrolled hypertension or diabetes, or other medical condition that would make participation hazardous	Self-report, clinical interview, abnormal ECG, Medical history, physical examination
5. Interest in treatment for cannabis use	Self-report, clinical interview
6. Current parole or probation	Self-report, clinical interview
7. Current pregnancy or lactation	Clinical interview, physical examination, pregnancy testing (serum HCG)

8. Recent history of significant violent behavior (past year)	Self-report, clinical interview
9. Current Axis I psychopathology requiring medical intervention (e.g., bipolar disorder, major depressive disorder, suicide risk, schizophrenia)	Clinical interview; diagnoses determined by a clinical interview via the SCID, as confirmed by the psychiatric evaluation

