10. Current use of any prescription or over-the-counter medication	Clinical interview, medical history, physical examination

Study Procedures

Provide a clear, concise narrative of study procedures with special attention to the subjects' involvement. Detail the overall study timeline and location of study procedures, list all interventions, assessments and interviews, estimate the duration of each procedure, provide dosing schedules, identify study personnel involved in each procedure, and provide credentials for relevant personnel. For complicated study designs, we strongly encourage attaching tables, flow-charts, and study algorithms.

General design: This within-subject study will have two 11-day inpatient phases, with one phase testing lorcaserin and the other phase testing placebo maintenance in counter-balanced order. In between the two inpatient phases, there will be a minimum 7-day outpatient period with no medication administration to provide time for medication clearance and the resumption of daily cannabis use. Inpatient phases will be preceded by two brief outpatient days of lorcaserin administration and a move-in day so that by Day 1 of each inpatient phase, participants will have achieved steady state conditions (3 days of 10 mg BID lorcaserin administration). On outpatient dosing days, participants will take their AM capsule under observation and will take their PM capsule (2030) at home. On the third day (move-in day), they will take their AM capsule under observation and then receive their PM capsule after moving into the laboratory. While inpatient, AM and PM capsules will always be administered under observation.

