Outpatient Dosing Visits: Participants will undergo two outpatient dosing visits immediately prior to each inpatient phase. On outpatient dosing days, participants will be administered capsules (lorcaserin or placebo, depending on phase) at 0900 under observation and will take their PM capsule (2030) at home. During outpatient dosing visits and move-in day, research staff will measure vital signs, urine toxicology, conduct at Timeline Followback and document any reported side effects from the medications. Staff will also ask about any medication or dietary supplement use. Participants will move into the residential laboratory (NYSPI, Division on Substance Use) the morning of the third outpatient dosing visit. They will be given the option to contribute a DNA sample on move-in day. We will over-enroll during the first outpatient phase, starting up to 7 individuals on medication, in order to ensure that we will have the maximum number of participants that can stay in the residential laboratory (n=4) on move-in day.

Inpatient Phase: Immediately before the onset of each new medication phase, female participants will have a urine pregnancy test. The overall design and daily inpatient schedule is outlined in the attached tables (Table 1 and 2). We will assess vital signs each morning. On move-in day, we will instruct participants on how to smoke marijuana using the paced puffing procedure and will inform them that this is the strength available for self-administration. On the first full inpatient day (day 1), participants will smoke experimenter-administered cannabis 6 times (3 puffs/occasion). The purpose of this day is to standardize cannabis exposure prior to abstinence initiation. During the next 3 days (days 2-4; Table 1), participants will have the opportunity to purchase individual puffs of cannabis at \$2/puff, at 6 time points. This measures the reinforcing effects of cannabis under nonabstinent conditions, and will reveal whether a medication facilitates *abstinence initiation*. On day 5, cannabis will be experimenter administered at 6 time points in order to again standardize cannabis exposure and assess medication effects on cannabis subjective ratings. On days 6-8, no cannabis

Table 1: Representative Dosing Schedule

Day	Outpt (2 days)	Move-in	1	2	3	4	5
Phase	Medication Initiation	Predose	Subj-effects	Abstinence Initiation*	→		Subj-effects
Cannabis	none	7.0%THC	7.0%THC	7.0%THC	7.0%THC	7.0%THC	7.0%THC
Lorcaserin (mg BID)	10	10	10	10	10	10	10

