Day	6	7	8	9	10	11	Move-out
Phase	Withdrawal	→		Relapse	→		
Cannabis	none	none	none	7.0%THC	7.0%THC	7.0%THC	
Lorcaserin (mg BID)	10	10	10	10	10	10	

Outpt=Outpatient. *Order of abstinence initiation and withdrawal/relapse phases will be counter-balanced.

will be available. This period will assess medication effects on cannabis withdrawal. For the remaining inpatient days (days 9-11; Table 1), participants will be presented with 6 opportunities throughout the day to purchase individuals puffs of cannabis (\$7 first puff, \$1 subsequent puffs). These days provide a laboratory measure of cannabis relapse. Money spent on cannabis during the inpatient phase is deducted from the total study pay at the end of the study. Participants will move out on Day 12 after passing the field sobriety test. Note, we will counter-balance the cannabis self-administration and relapse conditions across inpatient phases so participants are not able to predict the study schedule in the subsequent inpatient phase; sometimes the withdrawal and relapse condition will occur first and the abstinence initiation condition will occur second. Throughout each day, participants will wear an Actiwatch Activity Monitoring System (Actiwatch: Respironics Company, Bend OR), which tracks gross motor activity, and provides objective data on the number of hours slept and the number of awakenings (Perez et al., 2008). The Actiwatch is the size of a wristwatch. It will be removed briefly each evening in order to download that day's data. Participants will also give a urine sample each morning upon awakening. We will conduct a urine toxicology twice/week; we will also measure extracellular vesicles in urine on certain inpatient days to look for biomarkers of recent marijuana use (potential preliminary data for future grant funding).

Table 2: Inpatient Schedule

0815	Wake up	1315	Task and Subjective-effects Batteries
	Subjective-Effects Battery	1415	Choice of 0, 1, 2, or 3 puffs
	Sleep questionnaire	1430	Cannabis administration
	Tobacco Cigarettes	1445	Task and Subjective-effects Batteries
	Weigh In, BP/HR Receive Food Boxes	1545	Choice of 0, 1, 2, or 3 puffs
0830	Medication administration	1600	Cannabis administration
0900	Task and Subjective-effects Batteries	1615	Task and Subjective-effects Batteries
0945	Choice of 0, 1, 2, or 3 puffs	1700	Recreation period starts
1000	Cannabis administration*	2030	Medication administration
1030	Task and Subjective-effects Batteries	2145	Choice of 0, 1, 2, or 3 puffs

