NYSPI Protocol Number: 7475

Protocol Title: Effect of Lorcaserin on Cannabis Withdrawal and Self-administration

Principal Investigator: [name]

NCT03253926

Date: 06/29/2022

Data Analysis Plan

Repeated measures analyses of variance including two within-subject factors (medication dose, and inpatient day) with planned comparisons were used to determine the effects of lorcaserin, relative to placebo, on (primary outcome) cannabis self-administration under abstinent and non-abstinent conditions and (secondary outcome) subjective effects following controlled cannabis administration. Other secondary outcomes included the following: number of cannabis puffs that were self-administered, daily peak subjective-effects ratings, drug craving, objective and subjective sleep measures, food intake (total energy intake, percent macronutrient [fat, protein, and carbohydrate]), body weight, blood pressure and heart rate. Significance was determined at $\alpha = 0.02$. Huynh–Feldt corrections were used. Note that repeated-measures, within-subject designs result in substantial correlations between levels and are a powerful statistical approach. Based on a previous study from our group, a sample size of 15 study completers provides >90% power to detect changes in cannabis self-administration and subjective effects as a function of lorcaserin versus placebo. Effects of lorcaserin on the frequency of side effects were assessed using sign test, a nonparametric test used to identify consistent differences between pairs of observations (lorcaserin vs. placebo).

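### Body weight is a secondary outcome, but no pre-dose weight is stated for either phase and the model has no baseline or period term, so the weight contrast loses precision and is open to carryover

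*Protocol*

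**What the plan says.** - **Outcome.** The SAP (Data Analysis Plan) ends its list of other secondary outcomes with "body weight, blood pressure and heart rate".
- **Start of dosing.** Protocol, Study Procedures, General design: "Inpatient phases will be preceded by two brief outpatient days of lorcaserin administration and a move-in day". The stated aim is that "by Day 1 of each inpatient phase, participants will have achieved steady state conditions".
- **Weighing.** The only weigh-in named is in the 0815 block of Table 2 (Inpatient Schedule), "Weigh In, BP/HR Receive Food Boxes", just before the 0830 capsule.
- **Outpatient and move-in visits.** "During outpatient dosing visits and move-in day, research staff will measure vital signs, urine toxicology", a Timeline Followback and side effects. Weight is not named, and vital signs are not defined.
- **Screening.** One exclusion applies to people who "have lost more than 10% of their body weight within the last 3 months", checked by history and physical examination. No recorded weight is stated.
- **Gap between phases.** "there will be a minimum 7-day outpatient period with no medication administration". No maximum is given, and the stated purposes are drug clearance and return to daily cannabis use.
- **Order and model.** Medication order is counter-balanced. The SAP uses a repeated measures ANOVA with two within-subject factors, medication and inpatient day, at alpha 0.02. It names no period, sequence or baseline term.

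**The concern.** Puffs and ratings are produced afresh in each phase. Body weight is a level that a participant carries from one phase to the next, and lorcaserin is approved for obesity, so weight may move in response to it. With no weight taken just before dosing in each phase, a participant's lorcaserin-minus-placebo difference in absolute weight includes whatever happened to that weight between phases.

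Two things are at stake. Individual between-phase change adds error to the contrast. And in lorcaserin-first participants, weight lost in phase 1 and not regained lowers the placebo-phase weights, which shrinks the contrast. Day 1 is an imperfect substitute baseline, because any effect of the first three dosing days is already in it.

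**Working it through.** **The plan's own figure.** There is none for weight. The SAP's claim of more than 90% power with 15 completers covers self-administration and subjective effects. At two-sided alpha 0.02 it needs a standardised paired effect of about 1.04. No effect size or SD is given, so it can be neither reproduced nor refuted, and this point does not depend on it.

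**Timing (from the documents).** Dosing lasts 14 days (Risks, Lorcaserin) at two capsules a day: 14 × 2 = 28. Before Day 1 at 0815: 3 × 2 = 6 capsules. If the morning routine also applied on move-in day, at least 2 × 2 = 4 would already have been taken. By the Day 11 weigh-in 13 dosing days are complete, and Day 1 to Day 11 spans 10 of them: 10/13 = 77%.

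**Common drift.** If every participant's weight shifts by d between phases, the unadjusted mean contrast shifts by d × (difference in sequence sizes)/15. Per 1 kg of drift:
- 8:7 split: 1/15 = 0.067 kg
- 9:6 split: 3/15 = 0.20 kg
- 10:5 split: 5/15 = 0.33 kg

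The rest of the drift becomes error variance because there is no period term. In a simulation with a paired SD of 1 kg, d = 1 kg and an 8:7 split, type I error at nominal 0.02 fell from 0.021 to 0.001. The test becomes conservative, not anti-conservative.

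**Carryover.** Let a fraction λ of the weight effect persist through a later placebo phase. The absolute-weight contrast is then the true effect × (1 − λ × n/15), where n is the number treated with lorcaserin first. For n = 7 or 8:
- λ = 0.25: 88% or 87% of the true effect
- λ = 0.5: 77% or 73%
- λ = 1: 53% or 47%

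Counter-balancing does not remove this.

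**Individual change (all kg inputs assumed).** Take a day-to-day SD of 0.5 kg, 11 weigh-ins per phase, no common drift, and s = SD across participants of the between-phase change in level.
- Absolute weight: SD of the paired difference = √(s² + 2 × 0.5²/11) = √(s² + 0.045)
- Change from one pre-dose weight: √(2 × 0.5² + 0.045) = 0.74 kg for any s
- Pre-dose weight as covariate: slope b = s²/(s² + 0.5); SD = √(s² + 0.045 − s⁴/(s² + 0.5))

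| s (kg) | Absolute | Change score | Covariate | b |
|---|---|---|---|---|
| 0.5 | 0.54 | 0.74 | 0.46 | 0.33 |
| 1 | 1.02 | 0.74 | 0.62 | 0.67 |
| 2 | 2.01 | 0.74 | 0.70 | 0.89 |

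Estimating the slope and a period term from 15 pairs inflates the covariate column by about √(1 + 1/11) = 1.04, to 0.48, 0.64 and 0.73 kg. Multiplying by 1.035 gives the difference detectable at 90% power, for example 1.06 kg (absolute) against 0.64 kg (covariate column before inflation) at s = 1.

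The change score beats absolute weight only when s² > 0.5, that is, s above about 0.7 kg. With 1 kg of common drift and no period term, the absolute SDs rise to 1.14, 1.43 and 2.25 kg.

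**The case against.** A reader might infer that no participant has a drug-free weight and that all between-phase drift passes into the treatment effect. The documents do not support that.

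- Placebo-first participants are weighed on placebo throughout inpatient phase 1, before any lorcaserin.
- The protocol's lists are not exhaustive. The Physiological Measures list also omits weight, yet Table 2 schedules it beside blood pressure and heart rate. A weight at screening or with outpatient vital signs is therefore possible, though unstated. A screening weight could not serve as the phase 2 baseline.
- Counter-balancing cancels common drift apart from sequence imbalance.
- The medication-by-day comparison already in the ANOVA is unaffected by a different starting level in each phase. It loses only the change over the first three dosing days.

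It is also tempting to claim that subtracting a baseline always helps. It looks so only if the baseline weighing is given no measurement error; at s = 0.5 kg the change score is worse (0.74 against 0.54 kg). It can also be biased the other way: weight regained during a later placebo phase appears as gain on placebo and exaggerates the drug effect.

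Finally, body weight is absent from the protocol's aims, and the SAP is dated 2022 and written in the past tense, so an extra weighing may be too late for this trial.

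All of this stands. It narrows the point without removing it: the medication main effect on absolute weight still has no baseline or period adjustment, and carryover survives counter-balancing.

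**Conclusion.** The point holds as one of precision and carryover on a secondary outcome. No pre-dose weight is stated for either phase, and the planned model cannot absorb between-phase change. Drift bias in the mean is small with near-equal sequences (0.067 kg per 1 kg at 8:7).

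The loss of precision runs from negligible (s = 0.5 kg) to nearly threefold in SD (2.01 against 0.70 kg at s = 2 kg). That range rests wholly on an assumed day-to-day SD, an assumed between-phase SD and independent daily noise. The carryover loss depends on an unknown λ. The documents fix none of these, so the actual size is unknown. The steady-state lead-in is a deliberate choice and not an error. The primary outcome is unaffected, and this is a minor improvement.

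**What to change.** **Design (if participants are still to be dosed, or the design is reused).** Weigh each participant with the vital signs at the first outpatient visit of each phase, before the 0900 capsule.

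**SAP.** Analyse body weight with that phase's pre-dose weight as a covariate and with a period term, in preference to a simple change score. In paired form, regress the lorcaserin-minus-placebo difference in phase-mean weight on the difference in pre-dose weight and on sequence coded ±1 for period.

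**Participants already studied.** Use any weight recorded on the first dosing day, if taken before the capsule. If there is none, add a period term and report change from Day 1 beside the absolute-weight analysis, labelled as added and as excluding the first three dosing days.

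**Limitation to state.** Covariate adjustment removes only about a fraction b of a carried-over level, and regain during a later placebo phase can push the estimate the other way.

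**Cost.** One weighing per phase at a visit that already takes vital signs, a sentence or two in the SAP, and two degrees of freedom. An outpatient weight is slightly noisier than an 0815 inpatient weight; the covariate slope allows for that, whereas a change score would carry the noise in full.

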NYSPI Protocol Number: 7475

Protocol Title: Effect of Lorcaserin on Cannabis Withdrawal and Self-administration

Principal Investigator: [name]

NCT03253926

Date: 06/29/2022

Data Analysis Plan

Repeated measures analyses of variance including two within-subject factors (medication dose, and inpatient day) with planned comparisons were used to determine the effects of lorcaserin, relative to placebo, on (primary outcome) cannabis self-administration under abstinent and non-abstinent conditions and (secondary outcome) subjective effects following controlled cannabis administration. Other secondary outcomes included the following: number of cannabis puffs that were self-administered, daily peak subjective-effects ratings, drug craving, objective and subjective sleep measures, food intake (total energy intake, percent macronutrient [fat, protein, and carbohydrate]), body weight, blood pressure and heart rate. Significance was determined at $\alpha = 0.02$. Huynh–Feldt corrections were used. Note that repeated-measures, within-subject designs result in substantial correlations between levels and are a powerful statistical approach. Based on a previous study from our group, a sample size of 15 study completers provides >90% power to detect changes in cannabis self-administration and subjective effects as a function of lorcaserin versus placebo. Effects of lorcaserin on the frequency of side effects were assessed using sign test, a nonparametric test used to identify consistent differences between pairs of observations (lorcaserin vs. placebo).

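### The stated ANOVA for this two-phase crossover has no phase term, so any shift between phases stays in the error term and, when completers per order are unequal, partly in the estimate

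*SAP*

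**What the plan says.** The protocol (Study Procedures, General design) describes a within-subject study with two 11-day inpatient phases, "with one phase testing lorcaserin and the other phase testing placebo maintenance in counter-balanced order". At least 7 days without medication separate the phases. Under Inpatient Phase, the order of the self-administration and withdrawal/relapse blocks is also varied, "so participants are not able to predict the study schedule in the subsequent inpatient phase".

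The SAP is one paragraph, in the past tense. Its model is "Repeated measures analyses of variance including two within-subject factors (medication dose, and inpatient day"), with planned comparisons, Huynh–Feldt corrections and a significance level of 0.02. It states that "a sample size of 15 study completers provides >90% power", citing a previous study by the same group without an effect size or SD. Neither document names a phase, period, order or sequence term.

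**The concern.** In Table 1 of the protocol, inpatient day runs from 1 to 11 inside each phase. It identifies the day within an admission, not the first or second admission. Phase is a separate within-subject variable, and the model omits it.

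Each participant's lorcaserin-minus-placebo difference is the drug effect plus the phase shift if lorcaserin came second, or minus the shift if it came first. Counterbalancing cancels the shift in the average only when the two orders are equally represented. It never removes the shift from the spread of the differences, which is the error term for the medication test.

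Two things are at stake. With orders nearly equal, the loss is power, in a study of 15 completers tested at 0.02. With clearly unequal orders, the estimate is also biased. Balance among completers is not secured: the sample size is set in completers, no rule keeps the orders balanced, and the protocol says "We will over-enroll during the first outpatient phase, starting up to 7 individuals on medication" for four residential places.

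**Working it through.** **Inputs from the documents.** Two-phase crossover with counterbalanced order (Protocol, General design); 15 completers, significance level 0.02 and a claim of more than 90% power (SAP).

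**Assumptions.** Two-sided test. Phase shift π (phase 2 minus phase 1) of 0.25, 0.5 or 1.0 SD of the within-person difference, constant over days. Completers per order n1:n2 of 8:7 to 11:4.

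**The plan's own figure.** The power claim cannot be reproduced, because no effect size or SD is given. A paired t-test is equivalent to the F test for a two-level medication factor. With 15 pairs at two-sided 0.02, 90% power needs an effect of 1.035 SD (noncentrality 1.035 × √15 = 4.01 on 14 df). That effect is used below.

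**Model.** D_i = τ + s_i·π + e_i, where D_i is lorcaserin minus placebo, s_i is +1 if lorcaserin is in phase 2 and −1 if in phase 1, and e_i has SD 1.

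**Without a phase term**
- Bias in the mean difference = π(n1 − n2)/15. This is 1/15 of the shift at 8:7, 3/15 at 9:6, 5/15 at 10:5 and 7/15 at 11:4.
- Expected error variance = 1 + π²[1 − ((n1 − n2)/15)²] × 15/14. At 8:7 with π = 0.5: 1 + 0.25 × 0.9956 × 1.0714 = 1.27. With π = 0.25 it is 1.07, and with π = 1.0 it is 2.07.

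**With a phase term.** The estimate is the plain average of the two order-group means, on 13 df, with SE = √[(1/n1 + 1/n2)/4]. At 8:7 this is √(0.2679/4) = 0.2588, giving noncentrality 1.035/0.2588 = 4.00 and power 89.3% whatever the shift. There is no bias, and type I error is 2.0%.

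**Results.** Unadjusted figures are simulated; the two power values are for a shift favouring / opposing the drug effect.

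| Split | Shift (SD) | Power, no phase term | Power, phase term | Type I error, no phase term |
|---|---|---|---|---|
| 8:7 | 0.25 | 89.4 / 87.4% | 89.3% | 1.7% |
| 8:7 | 0.5 | 86.1 / 80.5% | 89.3% | 1.1% |
| 8:7 | 1.0 | 68.0 / 51.0% | 89.3% | 0.2% |
| 10:5 | 0.5 | 94.1 / 66.9% | 85.3% | 2.6% |
| 11:4 | 0.5 | – | 80.0% | 4.4% |
| 11:4 | 1.0 | – | 80.0% | 7.2% |

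The 94.1% at 10:5 is not a gain: one third of the shift has been added to the drug effect.

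**Break-even at 8:7.** At a shift of 0.2 SD, unadjusted power averaged over the two directions is 89.1%, against 89.3% adjusted. Below about 0.2 SD the phase term costs slightly more than it returns; above that it pays.

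**The case against.** The strongest reply is that no harm can be shown from the documents. Shift, split, effect size and SD are all assumed, and with no shift the omission costs nothing. This stands, and it is why the result is given as a range.

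Near balance the unadjusted test is conservative, so a positive finding there is not undermined. At 9:6 type I error is 1.9%, 1.5% and 0.6% for the three shifts. This also stands.

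The worst cells are unlikely if dropout is unrelated to order. Assuming 20 to 30 starters allocated equally, 15 completers split 10:5 or worse with probability 3–14%, and 11:4 or worse with 0–3%. A 1.0 SD shift would nearly equal the assumed drug effect. The over-enrolment concerns filling beds before any inpatient outcome, and nothing says that losses depend on order.

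The SAP claims more than 90% power, and a larger effect leaves more room. At 1.2 SD (96.8% power with no shift), a 0.5 SD shift at 8:7 still leaves 92–95%; a 1.0 SD shift leaves 72–84%.

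The protocol also acts against a shift, through the gap between phases and the varied block order. These measures may reduce one, but prices and the daily timetable repeat at the second admission, so zero cannot be taken for granted.

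Finally, a list of within-subject factors does not strictly exclude order as a between-subject factor, and a one-paragraph summary may leave out a term that was fitted. No such term is named, however, and one sentence would settle it.

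**Conclusion.** The concern holds. The stated model omits phase, so a shift between admissions inflates the error term. At exactly 15 completers equal orders are impossible, so at least 1/15 of the shift enters the estimate.

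Near balance the harm is lost power, not false positives: at 8:7, about 3–9 points for a 0.5 SD shift (89.3% against 86.1% and 80.5%) and 21–38 points for 1.0 SD (against 68.0% and 51.0%). Material bias needs a clearly uneven split, and type I error well above 2% needs about 11:4.

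These sizes rest on assumed shifts and splits, a two-sided test, an effect calibrated to exactly 90% power, and no effect of the counterbalanced block order, which is also unmodelled. The omission does not invalidate the analysis. It is a weakness that should be corrected because the correction is cheap.

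**What to change.** Add inpatient phase (1 or 2) as a fixed effect. Equivalently, analyse each participant's lorcaserin-minus-placebo difference with medication order as a between-subject factor, and estimate the drug effect as the equally weighted mean of the two order groups. The second form suits the ANOVA framework, since each participant fills only two of the four medication-by-phase cells. Report completers per order. If results are already available, as the SAP's past tense suggests, present this beside the stated ANOVA as a sensitivity analysis; if order was in fact modelled, say so.

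No new data are needed. The cost is one error degree of freedom (14 to 13). If there is no shift at all, power falls from 90.0% to 89.3% at 8:7, 88.1% at 9:6, 85.3% at 10:5 and 80.0% at 11:4. The effect detectable with 90% power rises from 1.035 SD to 1.046, 1.066, 1.107 and 1.180 SD respectively.

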Lorcaserin: Lorcaserin is well tolerated, with no evidence of the side effects commonly associated with 5HT2b or 5HT2a receptor agonists, e.g., abuse, hallucinations, cardiac valve disease (see Smith et al., 2010; Fidler et al., 2011; Shram et al., 2011). Transient and mild side effects include headache, dizziness, fatigue, nausea, dry mouth, constipation, cough, and back pain (Product label; Smith et al., 2010). Participants will be warned of rare but serious side effects include agitation, confusion, hallucinations, irregular heartbeat, depression, thoughts of suicide, and for men, an erection lasting longer than 4 hours. They will also be warned that they should use caution if they drink alcohol, drive a motor vehicle or operate heavy machinery until they know how the medication affects them (although they will be inpatient for all but 2 of the 14 days they take the medication). Participants will not be taking any medications, but will be warned not to take any dietary supplements such as St. John's Wort, tryptophan and drugs that impair metabolism of serotonin, such as dextromethorphan since serotonin syndrome, a potentially life-threatening drug reaction, can occur when two drugs that affect the body's level of serotonin are taken together. They will also be warned about the potential for heart valve problems and changes in white and red blood cells.

Given that only healthy participants will be enrolled and will only receive an active dose of lorcaserin for 14 days, these rare side effects are even less likely. In clinical trials of 1-year duration: 2.4% of patients receiving lorcaserin and 2.0% of patients receiving placebo developed echocardiographic criteria for valvular regurgitation at one year. Decreases in white blood cell count were reported in 0.4% of patients treated with lorcaserin as compared to 0.2% of patients treated with placebo. Decreases in red blood cell count were reported by 1.3% of patients treated with lorcaserin as compared to 1.2% treated with placebo. The participants will be inpatient in a closely-monitored residential laboratory setting within the NY State Psychiatric Institute for 12 of the 14 days they are taking lorcaserin so we will monitor them closely throughout their participation. We will do an ECG at screening and at the end of the study, and assess vital signs each day.

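### With 15 pairs and a 0.02 level, the sign test for reported side effects is too weak for a non-significant result to count as evidence of tolerability

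*SAP*

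**What the plan says.** The SAP is one paragraph, the Data Analysis Plan. On reported side effects it says "Effects of lorcaserin on the frequency of side effects were assessed using sign test" and describes the test as "a nonparametric test used to identify consistent differences between pairs of observations (lorcaserin vs. placebo". It sets a single significance level, 0.02, and names no separate level for side effects. It does not say whether the sign test is one- or two-sided, how ties are handled, or what makes up a pair (presence of one side effect, a count of reports, or a total per symptom). No effect estimate or interval is planned for side effects.

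The sample-size sentence says that 15 completers "provides >90% power to detect changes in cannabis self-administration and subjective effects as a function of lorcaserin versus placebo". Side effects are outside that statement.

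The protocol (Study Procedures, General design) is a two-phase crossover, "with one phase testing lorcaserin and the other phase testing placebo maintenance in counter-balanced order", so each completer supplies one lorcaserin/placebo pair. Its Risks section names the effects to expect: "Transient and mild side effects include headache, dizziness, fatigue, nausea, dry mouth, constipation, cough, and back pain". It gives no rates for them.

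**The concern.** A sign test uses only participants whose two phases differ; ties carry no information. With 15 participants and a side effect that many never report, few informative pairs remain, and a 0.02 level demands near-unanimity among them. For an efficacy claim, a strict level guards against a false positive. For harms, the same strictness raises the chance that a real effect goes undetected. If the tolerability of lorcaserin is then read from the p-value, the reading may reflect the limits of the test more than the data. For example, headache in 6 of 15 participants on lorcaserin only, and in none on placebo only, would not reach two-sided significance at 0.02.

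**Working it through.** **The plan's own figure.** The power above 90% cannot be reproduced, because no effect size, standard deviation or within-subject correlation is given. As a rough guide, a paired t-test with n = 15 and two-sided 0.02 needs a standardized paired difference of about 1.03 for 90% power. The figure does not cover side effects, so there is no stated power to compare with the results below.

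**Inputs.** From the SAP: n = 15 pairs and level 0.02. Assumed: a two-sided exact test with participants as pairs (alternatives below); side-effect rates; independence of reports between phases.

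**Step 1: which results reach 0.02.** With x pairs in the lorcaserin direction, y in the placebo direction and m = x + y, the exact two-sided p is 2 × P(X ≥ x), where X is binomial (m, 0.5).

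- 5 to 0: 2/32 = 0.0625
- 6 to 0: 2/64 = 0.031
- 7 to 0: 2/128 = 0.0156, the first below 0.02; 7/15 = 47%
- 9 to 1: 2 × 11/1024 = 0.0215
- 10 to 1: 2 × 12/2048 = 0.0117, the minimum with one reversal
- With two reversals the minimum is 12 to 2: 2 × 106/16384 = 0.0129

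**Step 2: sidedness.** One-sided, 6 to 0 gives 1/64 = 0.0156, so the minimum falls to 6 of 15 (40%).

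**Step 3: chance of significance.** Let a be the lorcaserin rate and b the placebo rate. Under independence, P(lorcaserin only) = a(1 − b) and P(placebo only) = b(1 − a). For 30% versus 5% these are 0.30 × 0.95 = 0.285 and 0.05 × 0.70 = 0.035, leaving 0.680 tied. Trinomial probabilities for n = 15 are summed over all results significant in the lorcaserin direction.

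| Lorcaserin vs placebo rate | Two-sided 0.02 | One-sided 0.02 |
|---|---|---|
| 30% vs 5% | 7% | 16% |
| 40% vs 5% | 24% | 40% |
| 50% vs 5% | 47% | 66% |
| 30% vs 0% | 13% | 28% |
| 40% vs 0% | 39% | 60% |
| 60% vs 0% | 91% | 97% |
| 40% vs 10% | 14% | 26% |
| 60% vs 10% | 52% | 72% |

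For n = 15, a two-sided test at 0.05 has the same rejection region in the lorcaserin direction as a one-sided test at 0.02, so the last column serves for both.

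**Step 4: what estimation would show.** For 6 to 0 the paired difference is 6/15 = 40%, with a 95% score interval of 11% to 64%. At a difference of zero the score statistic is (x − y)/√(x + y) = 6/√6 = 2.45, above 1.96.

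**Step 5: the pairing unit.** If participants are paired on counts of reports, the minimum of 7 non-tied pairs in one direction stands, but those participants need not be free of the effect on placebo. If symptoms are the pairs, the threshold no longer refers to participants. The symptoms then come from the same people, so the pairs are not independent and the p-value is not valid.

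**The case against.** Several stronger readings are tempting, and the documents do not support them.

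- A reader might infer that common side effects will be reported as showing no difference. The SAP has no such rule and does not exclude reporting counts. Nor is non-significance certain: 60% versus 0% has 91% power.
- A reader might infer that the sign test is the only harms analysis. It is the only analysis of reported side effects. Blood pressure, heart rate, body weight, sleep and peak subjective ratings are in the repeated-measures ANOVA.
- A reader might infer that 0.02 was chosen for efficacy. The SAP gives no reason for it. The level is stated among the ANOVA sentences, so applying it to the sign test is the natural reading of a single level, but still an inference.
- A reader might treat 47% as a fixed barrier. It depends on a two-sided test with participants as pairs, neither of which is stated.

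Two further objections carry weight. First, low power for single side effects is inherent at n = 15; a two-sided level of 0.05 still gives only 16%, 40% and 66% for the three 5%-placebo scenarios. That stands, and it favours estimation over a different cut-off. Second, setting a 95% score interval against an exact test at 0.02 is not like for like: at 4 to 0 the statistic is 4/√4 = 2.00, so the interval excludes zero although the exact p is 2/16 = 0.125. The interval is indeed approximate with few discordant pairs. However, under equal discordance of 5% to 25% each way (five levels checked, n = 15) it wrongly excludes zero at most about 4.9% of the time, so it is not anti-conservative in that range.

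**Conclusion.** The concern holds in limited form. For side effects affecting about 20% to 40% of participants on lorcaserin, the planned test is more likely than not to miss a real difference, on either sidedness for most of the rates considered. At 50% versus 5%, the two-sided test at 0.02 is close to a coin toss. A non-significant result is therefore weak evidence of tolerability. The thresholds (7 to 0, or 10 to 1; 6 to 0 if one-sided) are exact once sidedness and pairing unit are fixed. The power figures rest on assumed rates and independence between phases, because the documents supply neither. The consequence is confined to how reported side effects are interpreted; the primary outcome is not affected. It should be corrected, because the decision rule is weak and a more informative summary is available from data the plan already collects.

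**What to change.** Amend the side-effect sentence of the SAP as follows.

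1. The participant is the pairing unit. For each side effect, and for any side effect, the pair is presence or absence in the lorcaserin and placebo phases.
2. Report, for each, the number of participants affected per phase, the two discordant counts (lorcaserin only, placebo only), and the paired difference in proportions with a 95% score interval, noted as approximate when discordant pairs are few.
3. State that the 0.02 level is not used to decide on side effects, and that a non-significant sign test is not evidence of no effect.
4. Keep the sign-test p-value, specified as two-sided, only as a supplement.

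The cost is a few sentences and one table, with no new data. The SAP is written in the past tense, but this is a change in reporting and can still be made. The downsides are wide intervals and no multiplicity control across side effects, so an isolated interval that excludes zero should be read as a signal and not as a confirmed effect.
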